## 5. STUDY SAFETY

**5.1 SAFETY PROCEDURES.** The FAST RCTs will assess *standard prenatal treatment* that has been used for decades because the fetus suffers from a life-threatening yet treatable cardiac condition and other management options including direct treatment or premature delivery are considered more invasive, more harmful, or both. Perinatal demise is not an unusual outcome of hydropic fetuses with SVA, irrespective of the choice of treatment. Health Canada, FDA (US) and MHRA (UK) have approved all three RCT sub-studies. There is extensive data on the safe use of the study agents for this indication. Minor drug-related maternal AEs are not infrequent [monographs], but maternal SAEs owing to fetal antiarrhythmic drug therapy have not been reported. However, virtually all antiarrhythmics have proarrhythmic potentials to provoke new or exacerbate existing

arrhythmias. This risk increases with toxic drug levels, maternal heart disease, preexisting ventricular arrhythmia, and hypokalemia.

Procedures for study participants to minimize the risk of SAEs include:

- only mothers without serious health and pregnancy concerns other than fetal SVA are eligible for participation in RCT sub-studies (**see 7**);
- the primary physician and participant both are informed about the assigned drug therapy from the time of randomization to study end (open label trial);
- drug dosages will be used that are considered to be safe and effective, thus avoiding toxic levels (digoxin) and excessive QTc prolongation >0.5 (sotalol); d) concomitant medication (7.6.2) that may interact with a study drug are not to be used or, if no alternative exists, used with caution during the trial; and
- initiation of therapy is recommended in-hospital to monitor maternal/fetal heart rates and wellbeing, followed by serial outpatient encounter once arrhythmia control is achieved.

**5.2 ADVERSE EVENT ASSESSMENT AND DOCUMENTATION.** A main objective of FAST RCTs is patient safety. This is accomplished by the systematic recording of AEs.

**Adverse Event (AE):** is defined as **any untoward medical occurrence of a symptom that may or may not have a causal relationship with the treatment used.** Examples include a rash noted during a physical exam, abnormal lab results, or a change from a baseline condition.

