## 7. CONDUCT OF THE RCTs

The Table of Events below summarizes the different study steps from the time of prenatal identification and randomization to study end as they relate to the RCT sub-studies.

Procedures and Tests	Pre-treatment	Fetal Treatment		Postnatal Birth to 30(+) days
		Day 1	Day 2 - Birth	
Fetal echo: Diagnosis -SVA (M-mode; Doppler) - Fetal state	X diagnosis and data ⬆ Images within 1 week recommended		X data each visit ⬆ if changed	
Maternal 12-lead ECG	X required prior to treatment start ⬆		X recommended within 1 week of treatment start and repeated at every significant change in treatment/increase in dose ⬆ if changed	
Maternal exams: - BP, HR	X		X recommended within 1 week of treatment start and during maintenance therapy	
Maternal tests: - K, Ca - serum creatinine	X			
Maternal and pregnancy history	X			
Maternal consent	X			
Eligibility Assessment - PI	X			
Randomization	By sites in REDCap			
Hospitalization		Recommended	If indicated	If indicated
Treatment initiation		X		
Review of current treatment - Drugs, dosages, intervals			X each visit	X
Review of clinical findings			X each visit	X
Review of test results - Digoxin level (if relevant)			X each visit	
- Home fetal heart rate monitor (FHRM)			⬆ or enter data	
Adverse event assessment			X each visit	X
Compliance assessment (1st line therapy)			X each visit	
Review of prenatal outcome			X at birth/IUD	
Neonatal 12-lead ECG in sinus rhythm				X ⬆
Neonatal 12-lead ECG tracing in SVA				X ⬆ if present
Review of neonatal outcome				X at 30(+)days/NND
Review of maternal outcome				X

X = data entry into REDCap, ⬆= uploaded in REDCap

Patient identification, data entry, eligibility screening, randomization (Pre-treatment) and treatment initiation (Day 1) are to occur on the same day if there is an immediate need of fetal treatment.

**7.1 PATIENT IDENTIFICATION.** The site investigator will be responsible for identifying and recruiting RCT participants and conducting the study at the participating center. The investigator will inform a patient who fulfills eligibility criteria about the study early on with the help of a *Patient Brochure*.

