**INCLUSION CRITERIA:**

- Mother has provided written informed consent to participate in the RCT
- Fetal AF *without* hydrops (RCT A) or SVT *without* hydrops (RCT B) or SVT *with* hydrops (RCT C)
- Tachyarrhythmia that is significant enough to justify immediate transplacental pharmacological treatment:
  - Tachycardia  $\geq 170$  bpm during  $\pm 100\%$  of time ( $\leq 30$  0/7 weeks of gestation)
  - Tachycardia  $\geq 180$  bpm during at least 10% of observation time
  - Tachycardia  $\geq 280$  bpm
  - Tachycardia with fetal hydrops
- Gestational age  $> 12$  0/7 weeks and  $< 36$  0/7 weeks at time of enrolment
- Untreated tachycardia at time of enrolment
- Singleton Pregnancy
- Healthy mother with  $\pm$  normal pre-treatment cardiovascular findings:
  - ECG within normal range (sinus rhythm; QTc  $\leq 0.47$ s; PR  $\leq 0.2$  s; QRS:  $\leq 0.12$  s; insignificant anomalies; isolated premature beats; isolated complete right bundle branch block; non-specific ST-T segment changes allowed)

- Maternal resting heart rate of 50 bpm or above
- Maternal systolic BP of 85 mm Hg or above

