- The mode of supply and dispensation of 1st line medication
- Home fetal heart rate monitoring (FHRM) offered to participants
- The documentation of de-identified study results in CRFs and REDCap
- Participant questionnaires (AEs and fetal heart rate monitor), medication diary, fetal heart rate monitoring log
- AE assessment and reporting
- Adherence rate to treatment assessment

**DATA DOCUMENTATION:** The table of events summarizes the study conduct and procedures

**PRENATAL.** Following randomization and treatment initiation, sites must upload *de-identified images* to REDCap of pre-treatment M-mode and/or Doppler still images, 2-dimensional images of the fetal abdomen, and 12-lead maternal ECG for review and confirmation of diagnosis by the FAST Trial Echo Core Lab. Moving clips confirming the fetal SVA mechanism should be sent via secure file transfer for Echo Core Lab review.

Following treatment initiation, it will be possible to document the result of up to 25 prenatal participant encounters in REDCap (from day 1 of treatment to birth or death). Pre-natal participant encounters during

maintenance therapy will occur every 1-3 weeks as clinically indicated/opinion of the Investigator. Information that is captured includes:

- Date of encounter → gestational age at encounter and total days of prenatal treatment
- Patient care: inpatient versus outpatient; methods of maternal-fetal surveillance
- Participant adherence to therapy (first-line therapy only)
- Maternal findings\*: Diagnoses; adverse symptoms (questionnaire); ECG; digoxin level
- Fetal findings\*: diagnoses; rhythm; atrial and ventricular rate; SVA characteristics; date of cardioversion; fetal state; cardiac function, AV regurgitation; umbilical venous flow, FHRM data (log)
- Current medication and treatment recommendations to next encounter
- Rationale of treatment modifications and adherence to Care Maps
- File uploads of new clinically relevant test results#: if relevant new findings, upload maternal 12-lead ECG, M-mode and/or Doppler of current rhythm.

\* = All data will be entered into CRFs and into REDCap. # = images of new, relevant results to be uploaded into REDCap (de-identified) or sent via secure file transfer.

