#### **SECONDARY OUTCOME**

- Proportion of participants with cardioversion over time
- Proportion of participants with treatment failure
  - Number of participants with treatment failure compared to number of participants with successful treatment.
  - Treatment failure is defined as one of the following:
    1. cross-over to another drug
    2. SVT/AF that persists to birth
    3. preterm birth
    4. death
- Cause of death (prenatal, postnatal)
- Proportion of participants with arrhythmia related death
- Average gestational age at birth
- Birth weight (z-scores)
- Average days of maternal and neonatal hospitalization related to SVA therapy
- Maternal prevalence of pregnancy/treatment-related AEs and outcomes
- Proportion of AEs / adverse outcomes (prenatal, postnatal)

The primary outcome measure is absolute (term delivery without tachyarrhythmia) with no room for interpretation. Secondary outcomes will be the time interval from treatment initiation to the beginning of permanent cardioversion, and once established, the freedom from SVA recurrence on maintenance therapy. Only the final outcome will be considered to classify cases. Cross-over to another agent, fetal demise, development of fetal hydrops, and delivery for SVA will be considered treatment failures. Any recurrence of fetal SVA after

documentation of a normal cardiac rhythm >24 hours by echocardiography will be classified as maintenance treatment failure.

**7.11 STATISTICAL ANALYSES.** All statistical analyses using SAS (SAS Institute, Cary NC) with standard settings will be performed by very experienced statistician from the Cardiovascular Data Management Centre (CVDMC) at SickKids. As a general precept, all 3 RCTs will be analyzed separately. RCT analyses will be performed on an *intention-to-treat basis*, although a separate subgroup analysis will be performed. Descriptive statistics for all study variables, for each study groups separately, will be created using means with standard deviation, median with inter-quartile range, and frequencies as appropriate. Baseline characteristics that should be equally distributed between groups through randomization (age at diagnosis, baseline fetal heart rate, incessant vs. intermittent SVA, maternal age) will be assessed in a test of randomization. The test of randomization will be performed using Fisher’s exact test for categorical variables and Student’s t-test (with Satterthwaite method for variance estimation) for continuous variables.

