The **PRIMARY OUTCOME** (proportion of term deliveries without SVA) will be a binary outcome (yes/no). For this type of outcome, the proportion of participants in each therapy arm will be compared using logistic regression models (PROC LOGISTIC) with likelihood ratio test to determine regression model fit, Wald chi-square test from maximum likelihood estimates (Fisher’s scoring technique) to determine statistical significance of the therapy arm and c-statistic from the regression model’s area under the curve (AUC) to measure model accuracy. Effect size estimate and standard error will be converted into odds ratio with 95% confidence (95% CI) limits to facilitate comparisons between the different trials.

**SECONDARY OUTCOME** will also be expressed as binary variables (incl. proportions of participants: requiring 2nd line therapy and 3rd line therapy; with SVA recurrence on maintenance therapy; delivery without SVA termination; death <1 month; etc.) will be assessed between the different therapy arms in the same way as the primary outcome. For outcomes with time dependent variables (proportion of participants with cardioversion over time; timing of mortality from initiation of therapy), Kaplan-Meier survival curves will be used to depict the event proportion over time for each group. Single phase parametric hazard regression model (PROC PHREG) will be used to compare the 2 therapy arms (with likelihood ratio test to determine regression model fit and maximum likelihood estimates chi-square to determine statistical significance of the therapy arm. Effect size estimate and standard error will be converted into hazard ratio with 95% CI to facilitate comparisons between the different trials. Finally, for outcomes with continuous variables (average gestational age at birth/birth weight z-score; average days of neonatal hospitalization related to SVA therapy), linear regression models using maximum likelihood estimates for parameter estimation will be used (PROC GENMOD: Akaike's information criterion (AIC) criterion to assess regression model fit; Wald chi-square test from maximum likelihood estimates). Effect size estimate and standard error will determine the difference between the therapy arms in the same original units of measurement as the outcome.

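### The cardioversion and mortality clocks start at first treatment rather than at randomisation, and no rule places participants who have no first dose, or an event before it, in the intention-to-treat comparison

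*Combined protocol and SAP*

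**What the plan says.** - **Time origin, cardioversion (section 7.10):** "Secondary outcomes will be the time interval from treatment initiation to the beginning of permanent cardioversion".
- **Time origin, mortality (section 7.11, secondary outcome):** the outcome is "timing of mortality from initiation of therapy". Both outcomes are to be shown as Kaplan-Meier curves and compared between arms with PROC PHREG.
- **Analysis principle (section 7.11):** the RCTs are analysed on an "intention-to-treat basis". The set is not defined further.
- **Masking (sections 2.6 and 5.1):** the trial is open label, and physician and mother know the assigned drug from randomisation onwards.
- **Gap between randomisation and first dose (note under the Table of Events, section 7):** the steps from identification to treatment initiation "are to occur on the same day if there is an immediate need of fetal treatment". Section 7.2 makes such a need an entry criterion for every participant: "Tachyarrhythmia that is significant enough to justify immediate transplacental pharmacological treatment".
- **Records (section 7.8, prenatal data documentation):** prenatal encounters are captured "from day 1 of treatment to birth or death".

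**The concern.** Randomisation makes the arms comparable at the moment of allocation. Both time-to-event outcomes are instead measured from a later event, one that happens after the drug is known and that need not happen at all.

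Two consequences follow. First, someone who never takes the first-line drug, or whose fetus converts, is delivered or dies before the first dose, has no time zero, and the plan does not say how that person enters the curves or the regression. Second, time spent in tachycardia between randomisation and the first dose is not counted. If one arm is slower to get started, the analysis cannot show it.

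Speed of cardioversion is a prominent secondary question. The introduction expects faster cardioversion to be associated with more normal term deliveries and with less perinatal mortality and morbidity. For mortality timing, the origin matters most in RCT C, since section 2.5 reports that 21% of hydropic SVT cases died in the earlier retrospective study.

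**Working it through.** **1. Does the time origin touch the plan's own design figure?** Section 3.2 gives 93, 89 and 93 per arm (RCT A, B, C). With a pooled-variance comparison of two proportions, two-sided alpha 0.05, power 80%, 1:1 allocation and no continuity correction:
- 30% vs 50% gives 93 per arm (RCT A and C)
- 55% vs 75% gives 89 per arm (RCT B)
- 186 + 178 + 186 = 550

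The stated figures reproduce exactly. They rest on the binary primary outcome, which has no clock, so moving time zero does not change them. The same holds for the binary secondary outcomes, including death before 1 month. No power or event count is given for the time-to-event outcomes.

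**2. How large a gap does the plan allow?** Set the note under the Table of Events beside section 7.2. The note makes a same-day start conditional on immediate need, and section 7.2 requires that need of every participant. Together they put the planned gap at under one day for essentially everyone. Neither says what happens in the analysis when this is not achieved.

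**3. What would a delay do?** The documents give no start delay and no never-start rate, so this is an illustration under assumptions.

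Inputs: the median times to SVT conversion in section 2.5 (Fig. 4), 3 days for digoxin and 4 days for flecainide. They come from a retrospective, non-randomised cohort of 75 SVT cases with and without hydrops, so they are not RCT B estimates. Exponential times are assumed.

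From first dose, hazard = ln 2 / median, so the hazard ratio (digoxin vs flecainide) is (ln 2 / 3) / (ln 2 / 4) = 4/3 = 1.33, whatever the delay.

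From randomisation, Cox hazard ratio by simulation (20,000 per arm, follow-up cut at 60 days):

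| Delay to first dose | Hazard ratio from randomisation |
|---|---|
| none | about 1.33 |
| 0.5 day, digoxin arm only | about 1.20 |
| 1 day, digoxin arm only | about 1.11 |
| 2 days, digoxin arm only | about 0.92 |
| 0.5 to 2 days, equal in both arms | about 1.30 to 1.32 |

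A constant shift applied to everyone leaves the order of events unchanged, so the last row differs from 1.33 only by simulation error and rounding.

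Conversion by day 5 for a 3-day median is 1 − 2^(−5/3) = 68.5% from first dose. With a one-day wait it is 1 − 2^(−4/3) = 60.3% from randomisation.

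**4. What would non-start do?** Suppose 2% to 5% never start (assumed). That is 0.02 × 89 = 1.8 to 0.05 × 93 = 4.7, or about 2 to 5 participants per arm. If all of them were in the digoxin arm and none ever converted, the hazard ratio from randomisation would be about 1.16 (2%) or 1.04 (5%) instead of 1.33. This is an extreme case: never-starters who convert spontaneously would pull the other way.

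**The case against.** The strongest reply is that the plan already closes most of the gap. Need for immediate treatment is an entry criterion, so the same-day provision should cover nearly all participants, and delays shared by the arms cancel. This stands, and it is why the expected effect is small.

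A reader might infer that participants who start late or never start are dropped. The documents do not say so, and section 7.11 commits to intention-to-treat. Some features do lean towards treated cases: section 3.2 counts sample size in treated cases, section 4.5 replaces withdrawals to reach evaluable numbers, and encounter records begin with treatment. But the fault is a missing rule, not a stated exclusion.

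A reader might also infer that the arms will differ in how fast treatment starts. The documents give little ground for that. Section 7.8 sets one supply rule for all first-line medication, and nothing reports a difference in acceptability. In RCT C both arms receive digoxin, oral or intravenous, plus an oral second drug. In RCT A and B digoxin may be given intravenously, but it may also be oral.

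The illustration uses the shortest medians available. For AF on sotalol section 2.5 gives 12 days, against which one day is 1/12, or about 8%. Part of the randomised-trial paragraph in section 4 is unreadable in the copy reviewed, so a further rule on start timing cannot be excluded.

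Finally, section 7.10 uses identical outcome measures for RCT and Registry subjects, and section 7.11 plans comparisons between them. Registry subjects have no randomisation date, so time from first dose has a legitimate use. That argues for keeping it as a second analysis, not as the basis of the randomised comparison.

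**Conclusion.** The point holds in a limited form. Both clocks have a stated origin after allocation, which does not fit the promised intention-to-treat analysis in an open-label trial. Participants with no first dose, or with an event before it, have no defined place in the time-to-event analyses.

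If the same-day provision is kept, the uncounted time is under one day, and the between-arm comparison is hardly affected when delays are similar. Bias needs a difference between arms in delay or non-start, for which the documents give no figure. The movement from 1.33 to about 1.11 rests on an assumed one-day delay in one arm and on exponential times with borrowed medians. It shows sensitivity and is not a forecast.

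The conclusion is confined to the timing of cardioversion and of mortality. The case for acting is that the correction costs little: it changes almost nothing if starts are prompt, and it protects the comparison if they are not.

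**What to change.** In sections 7.10 and 7.11, for the between-arm RCT comparisons:
- Set time zero for cardioversion and for mortality at randomisation, for every randomised participant, whether or not treatment started.
- Count events between randomisation and first dose. State that conversion, delivery or death in that interval is handled by the same rule as after the first dose.
- Keep time from first dose as a supportive analysis, and use it for comparisons with treated Registry subjects.

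The cost is mainly wording. Randomisation is done in REDCap (Table of Events, section 7.6), and the enrolment log holds the date and time of enrolment (section 7.1). The sponsor should confirm that the randomisation time itself is retained. Because prenatal encounter records begin with treatment, it should also confirm that an event before the first dose can be entered. The downsides are that reported times lengthen slightly by the start-up delay and that two origins must be reported and labelled. The sample size does not change.

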## 2.5 EFFICACY OF TRANSPLACENTAL THERAPY.

[figure not shown]
**PROSPECTIVE STUDY.** There are no other prospective randomized studies of fetal SVA therapy to date.

**RETROSPECTIVE STUDIES.** Retrospective studies report inconsistent success rates for all 1st line agents in treating fetal SVA. In studies (total n=226) using oral **digoxin** monotherapy, in-utero cardioversion has been reported in 50% to 100% of SVA *without* hydrops, but in <20% of SVA *with* hydrops. **Flecainide** (n=70) has resulted in sinus rhythm in 58% to 100% of SVA cases *without* hydrops and in 43% to 58% of those *with* hydrops. **Sotalol** (n=56) has been successful in 40% to 100% of SVA *without* hydrops, and in 50% *with* hydrops. While the studies confirm that there is no single medication that can convert all fetal SVAs to a normal rhythm, direct comparisons of study results is impossible as study cohorts varied in disease severities, definitions of treatment success, drug doses, schedules, and many other factors. Data on the impact of the same agents as 2nd line monotherapy or in combination to treat therapy-resistant SVA is largely unavailable.

**DRUG COMPARISONS.** The only study to directly compare transplacental drug therapies by [name] et al., an initiator of the FAST Therapy Trial, represented the experience of 3 sites, each using a different 1st line agent. An adverse primary outcome, defined as a) preterm delivery, b) perinatal death, or c) persistent SVA to birth, was documented in 45% of 75 treated SVT cases (outcome a) 32%; b) 8%; c) 5%) and 58% of 36 treated AF cases (a) 50%; b) 3%; c) 6%), and was mainly related to *incomplete SVA control at the time of the event*. However, [name]'s study also demonstrated that the fetal response to treatment independently depended on the *SVA pattern, fetal state* and the *choice of 1st line therapy*. AF [Fig. 1] and fetal hydrops [Fig. 2] were independently associated with

[figure not shown]

**Fig. 1. Freedom from termination of fetal SVT vs. AF despite drug treatment (n=111).** AF responded more slowly to drug therapy than SVT (HR=2; p=0.005). Cardioversion at 5 and 10 days was achieved in 50% and 63% of fetuses with SVT and in 25% and 41% of cases with AF.

[figure not shown]

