**Fig. 2. Freedom from termination of fetal SVT with and without hydrops (n=75).** Treatment failure was also more likely if SVT was associated with fetal hydrops (HR=1.8; p=0.04) at the time of diagnosis. It took more than twice as long (9 vs. 4 days) for conversion of 50% of SVT cases to a normal rhythm if fetuses were hydropic. 21% of the hydropic cases died.

[figure not shown]
lower cardioversion rates. On the other hand, 1st line monotherapy with sotalol resulted in faster/higher AF termination rates [Fig. 3] while flecainide or digoxin was superior in terminating SVT [Fig. 4] and in lowering tachycardia rates if SVA persisted [Fig. 5]. None of the agents as 2nd line therapy was associated with a greater rate of SVA termination although **sotalol** tended to be superior for AF. Once fetal SVA was converted to sinus rhythm, chronic drug therapy to birth with the drug(s) that successfully terminated the SVA was used to prevent recurrences. Recurrence of SVT and AF was documented in 8% and 15% of cases during the first month of maintenance treatment.

**Fig. 3. Freedom from termination of fetal AF (n=36):** For patients with AF, in multivariate models adjusted for arrhythmia pattern, 1st line sotalol was associated with a greater likelihood of AF termination compared with digoxin (HR: 5.4; p=0.05) or flecainide (HR: 7.4; p=0.03). Time to conversion of 50% was 12 days with sotalol, but not achieved with the other drugs before delivery.

**Fig. 4. Freedom from termination of fetal SVT (n=75):** For patients with SVT, in multivariate models adjusted for hydrops and SVT pattern, the use of flecainide (HR: 2.9; p=0.01) or digoxin (HR: 2.1; p=0.02) as 1st therapy were associated with increased likelihood of SVT termination compared to sotalol. The median time to conversion of 50% of cases was 3 days with digoxin, 4 days with flecainide but 12 days with sotalol.

**Fig. 5. Effects of 1st line treatment on tachycardia rates.** When incessant SVT (n=23) or AF (n=22) persisted to day 5 of treatment, ventricular rates were lowered more with flecainide and digoxin than with sotalol (p<0.001). This suggests that flecainide and digoxin are similarly effective in reducing the tachycardia to better tolerated rates while sotalol has no or only modest heart rate slowing effects.

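### Time to cardioversion: PROC PHREG's default tie handling will slightly shrink the hazard ratio, most in RCT B; section 7.11 should name Efron or exact ties

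*Combined protocol and SAP*

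**What the plan says.** Section 7.11 opens with a general rule on software: "All statistical analyses using SAS (SAS Institute, Cary NC) with standard settings will be performed by very experienced statistician". For outcomes that depend on time, including cardioversion over time, it draws Kaplan-Meier curves and then states: "Single phase parametric hazard regression model (PROC PHREG) will be used to compare the 2 therapy arms". The arm effect is judged by "maximum likelihood estimates chi-square to determine statistical significance of the therapy arm" and reported as a hazard ratio with a 95% confidence interval. No handling of tied event times is mentioned anywhere.

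Section 7.10 describes the endpoint: "Secondary outcomes will be the time interval from treatment initiation to the beginning of permanent cardioversion". In section 7.8, the list of data captured at prenatal encounters includes "SVA characteristics; date of cardioversion; fetal state", and counts treatment time in total days. No clock time of conversion is listed.

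On speed of conversion, the Fig. 1 legend in section 2.5 reports: "Cardioversion at 5 and 10 days was achieved in 50% and 63% of fetuses with SVT". The Fig. 4 legend reports, by drug: "The median time to conversion of 50% of cases was 3 days with digoxin, 4 days with flecainide but 12 days with sotalol". Fig. 2 gives the time to 50% conversion of SVT as 9 days with hydrops and 4 days without.

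**The concern.** If conversion is dated to the day and half of the fetuses convert within five days, many events share the same recorded time. The Cox partial likelihood then needs a rule for ties. Breslow's rule keeps every fetus that converts on a given day in the denominator for each of that day's events. When a sizeable share of the risk set converts on one day, this pulls the log hazard ratio toward zero. The model-based standard error hardly changes, so the test also loses power.

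Cardioversion over time is the first-listed secondary outcome and the most direct measure of drug effect. The hazard ratios are also meant to be compared across the three trials, and the shrinkage is larger in RCT B than in A or C. The loss can be avoided on the same data.

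**Working it through.** **1. The plan's own figure.** The documents give no hazard ratio, event count or power for cardioversion. The only stated calculation is for the binary primary outcome (section 3.2): two-sided 0.05, power 80%. With the pooled-variance formula n = [1.96·√(2p̄(1−p̄)) + 0.8416·√(p₁(1−p₁)+p₂(1−p₂))]² / (p₂−p₁)²:
- 30% vs 50%: (1.3579 + 0.5708)² / 0.04 = 93.0, so 93 per arm (RCTs A and C).
- 55% vs 75%: (1.3220 + 0.5551)² / 0.04 = 88.1, so 89 per arm (RCT B).

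Both match. Tie handling does not enter them.

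**2. How heavy the ties would be.** From Fig. 1, the SVT hazard over days 0 to 5 is −ln(0.50)/5 = 0.1386 per day. If that pooled curve applied to the 178 fetuses of RCT B, day 1 would hold 178 × (1 − e^(−0.1386)) ≈ 23 conversions, and the first five days 178 × 0.50 = 89, or about 18 per day.

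**3. The two rules.** For d events on one day, with risk set R and converting set D, the denominators are:
- Breslow: [Σ_R e^(βx)]^d
- Efron: Π_{j=0}^{d−1} [Σ_R e^(βx) − (j/d)·Σ_D e^(βx)]

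**4. Simulation.** Conversion times follow the section 2.5 curves. SVT hazards are 0.1386 to day 5, −ln(0.37/0.50)/5 = 0.0602 to day 10, and an assumed 0.03 afterwards. AF hazards are built the same way from 25% and 41%. Times are rounded up to whole days and tested by Wald chi-square at two-sided 0.05. Assumed: the true hazard ratio; proportional hazards; censoring uniform over days 14 to 120, or days 7 to 120 in the rows marked †. The RCT B rows use 3,000 trials each.

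| Scenario | True HR | Breslow: HR, power | Efron: HR, power |
|---|---|---|---|
| RCT B, pooled SVT curve | 1.38 | 1.37, 48.8% | 1.39, 52.2% |
| | 1.50 | 1.47, 67.0% | 1.49, 70.2% |
| | 1.60 | 1.57, 81.4% | 1.60, 84.6% |
| | 2.00 | 1.94, 98.7% | 2.01, 98.9% |
| RCT B, pooled SVT curve † | 1.50 | 1.47, 68.1% | 1.50, 72.8% |
| RCT B, constant hazard, median 3.5 days | 1.50 | 1.44, 67.3% | 1.50, 74.0% |
| RCT B, constant hazard, median 4 days in slower arm † | 1.50 | 1.44, 68.1% | 1.50, 75.5% |
| RCT A, 93 per arm | 1.50 | 1.493, 71.3% | 1.506, 72.6% |
| RCT C, 93 per arm | 1.50 | 1.485, 71.7% | 1.502, 74.0% |

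The 1.38 row is 2.9/2.1, the ratio of the flecainide and digoxin hazard ratios against sotalol in Fig. 4. On the pooled curve at 1.50, a fit to unrounded times gives 1.49 and 70.4%, so Efron on daily dates recovers essentially all of the loss.

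**5. Size on the log scale.**
- RCT B, pooled curve: ln(1.466) = 0.3825 against ln(1.5) = 0.4055, a shrinkage of 5.7%.
- RCT B, constant hazard: ln(1.444) = 0.3674, 9.4%. Using 1.44 from the † row: 0.3646, 10.1%.
- RCT A, against Efron: 1 − 0.4008/0.4095 = 2.1%. RCT C: 1 − 0.3954/0.4068 = 2.8%.

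**6. Hand check of the power.** On the pooled curve at 1.50 the mean standard error is 0.161 under both rules. The estimates vary with SD 0.157 (Efron) and 0.150 (Breslow).
- Efron: Φ[(0.4015/0.161 − 1.96) / (0.157/0.161)] = Φ(0.55) = 0.71.
- Breslow: Φ[(0.3825/0.161 − 1.96) / (0.150/0.161)] = Φ(0.45) = 0.67.

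Both agree with the simulation.

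**7. No difference between arms.** On the pooled SVT curve Breslow rejects in 4.3% of trials against 4.9% for Efron, and in a separate set 3.7% against 5.0%. The default is conservative.

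**The case against.** The strongest reply is that the effect is tiny. On the pooled curve the gap between the two estimates is 0.4015 − 0.3825 = 0.019, about 0.12 of a standard error of 0.161. At a hazard ratio of 2 the power loss almost vanishes. The plan sets no power target for cardioversion. All of this stands and fixes the grade as minor.

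Several stronger readings are tempting, and the documents do not support them:

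- *That the plan chose Breslow.* Ties are never mentioned. The default is a property of the software, and applying the general phrase about standard settings to it is an inference, though the natural one.
- *That 89 of 178 conversions by day 5 is the plan's figure for RCT B.* The 50% pools both hydrops states and three drugs, including sotalol, which is not used in RCT B. It is an extrapolation. The 4-day figure for non-hydropic SVT, and medians of 3 and 4 days for the RCT B drugs, suggest ties there could be heavier.
- *That the shrinkage is 9% to 10%.* A 4-day median is in Fig. 2, but a constant hazard is not. It implies 1 − 2^(−10/4) = 82% converted by day 10, against 63% in the pooled SVT data. This is an upper scenario. Dating late conversions at weekly visits also enlarges the loss, but that is interval censoring, which a tie option does not cure, and section 7.7 recommends in-hospital monitoring until cardioversion or rate control.
- *That the point is independent of the model label.* Section 7.11 calls the model single phase parametric while naming PROC PHREG, which as named fits a Cox model. In a truly parametric model this tie problem would not arise.

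The case report forms are not in the documents, so a clock time may be captured after all. If the arms barely differ, there is also little to shrink.

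**Conclusion.** The point holds as a minor one. If section 7.11 is followed literally, and PROC PHREG's default is Breslow, the cardioversion hazard ratio is pulled slightly toward 1. At an assumed true hazard ratio of 1.5 with daily dates, the size is:

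- RCT B, pooled SVT curve: about 5% to 6% of the log hazard ratio and 3 to 5 power points.
- RCT B, faster conversion: up to about 10% and 7 to 8 points.
- RCTs A and C: about 1 to 3 points.

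These figures rest on whole-day dating, proportional hazards, the assumed censoring and hazard after day 10, and the pooled historical curves. A reader might infer that the cardioversion comparison is invalid or that a false positive becomes more likely. Neither follows: the test is conservative, and the primary analysis and sample size do not depend on it.

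**What to change.** In section 7.11, specify PROC PHREG with TIES=EFRON (or TIES=EXACT) for time to cardioversion and any other time-to-event outcome dated in days. In the same sentence, replace the single phase parametric label with Cox proportional hazards. If a parametric model is truly intended, name that model and its procedure instead; the tie option is then not needed.

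The cost is one option in one SAS statement and a few words of text, with no new data and no extra participants. It should be settled before outcome data are examined, because changing the tie method afterwards would be an unplanned choice.
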